3.2.2.1 Serious Adverse Events

A serious adverse event (SAE) is any untoward medical occurrence that either results in death; is life threatening; results in persistent or significant disability or incapacity, requires in-patient or extended hospitalization; prolonged or existing hospitalization; is a congenital anomaly/birth defect in the offspring of a study participant; or is a medically important event that may jeopardize the participant or require intervention to prevent one of the above outcomes.

Data collection on the SAE will include the diagnosis of the AE, the intensity, the start and end dates, the outcome, the causality assessment with the vaccine, the seriousness criterion and the actions taken. Age and sex of the participant experiencing the SAE(s) will also be collected.

3.2.2.2 Adverse Events

An adverse event (AE) is defined as any untoward medical occurrence in a clinical trial subject to whom a vaccine has been administered; it does not necessarily have a causal relationship with the vaccine/vaccination. In this study, the recording AEs will be limited to injection-site reactions as site pain injection, redness, swelling, itchiness, infection, etc.

In addition to the diagnostic, the intensity, the start and end dates, the outcome, the causality assessment with the vaccine, the seriousness criterion and the actions taken. Age and sex of the participant experiencing the AE(s) will also be collected.

3.2.2.3 Immediate post vaccination reactions

Immediate reactions post-vaccination will be collected as other AE(s) from previous section.

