7.6.3 Administration of vaccine

PCV vaccine will be administered intramuscularly following the manufacturer recommendations. The vaccine will be administered in the deltoid region of either arm avoiding broken skin or injuries. It is recommended, but not required, that the injection be administered into the non-dominant arm.

The necessary equipment will be in place to manage eventual hypersensitivity reactions.

Vaccine preparation and administration as well as management of hypersensitivity reactions will be detailed in a study specific SOP.

The number of doses of vaccine administered at each site will be noted on tally sheets.

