7.10 Provision of medical care

Immediate reactions post-vaccination will be treated free of charge on-site by trained clinical staff. Free referrals to the nearest health center will be provided for any participants presenting to vaccination campaign sites with acute medical conditions necessitating clinical evaluation. Likewise, during the two cross-sectional surveys, household members with acute illness who need medical attention will be provided free referrals to the nearest health center.

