7.13 Expected Results

The overall project will present results for each of the primary and secondary objectives. For the main trial, results of prevalence of vaccine-serotype pneumococcus will be presented and compared. The results of the qualitative study will be presented in the form of a report. All results will be communicated as described below in section 13.6.

8 Safety reporting for Adverse Events and Serious Adverse Event

Data on Adverse Events (AEs) will be collected in a passive surveillance system for 7 days following vaccination. Data on Serious Adverse Events (SAEs) will be collected in a passive surveillance system for 28 days following vaccination.

A health professional from the study team will be based in the nearest health centre to the vaccinated villages for 28 days after vaccination activities, and will be the key notifiers of AEs and SAEs to the study team. Moreover, the community health workers from the vaccinated villages will be asked to act as a focal point and communicate to the study team any events that occur during the follow-up period. During the vaccination activities, caretakers will be informed about vaccine safety and will be asked to contact the community health worker or to attend the nearest health centre in case of a health problem.

Following, the International Conference on Harmonization (ICH) Guidelines for Good Clinical Practice, an adverse event (AE) is defined as any untoward medical occurrence in a clinical trial subject to whom a vaccine has been administered; it does not necessarily have a causal relationship with the vaccine/vaccination.

Definitions of AEs and grading will be specified in an SOP. In this trial, the recording of AEs will be limited to the evaluation of injection-site reactions (pain, tenderness, induration, infection, etc).

A serious adverse event (SAE) is any untoward medical occurrence that:

- Results in death.
- Is life threatening: if the participant was at risk of death at the time of the event; it does not refer to an event that hypothetically might have caused death if it were more severe.
- Results in persistent or significant disability/incapacity: if the event results in a substantial disruption of the participant's ability to carry out normal life functions.

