9.10 Participant privacy and confidentiality

The study staff will ensure that the participants' privacy is maintained.

No individual information will be collected at vaccination sites.

Pre- and post- survey participants will be identified by initials, age (and date of birth if known), sex and a unique ID number. All documents and electronic data will be stored securely and only accessible by study staff and authorized personnel. The study will make the information anonymous as soon as it is practical to do so.

The Investigator Site File and associated source documents will be retained for at least 10 years after the completion of the study. Written approval from the Sponsor will be obtained prior to destroying records.

All study related documents will be kept in locked cabinets at the study site. Filing cabinets with the study data and the participant information will be locked and accessed only by authorized persons from the Sponsor and Regulatory Authorities.

Participant personal data will be kept confidential and the privacy of all participants will be protected as far as permitted by law and following GDPR regulations. To ensure traceability and following

standard practice, nasopharyngeal samples will be labelled with participant initials, in addition to a unique ID number, sex and age. Only staff involved with the study conduct and local and international regulatory agencies may review these records.

10 Administrative aspects

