11.1 Overview

A Data Management team will be located at the study site. For surveys, all data will be collected on tablet computers using electronic CRFs (eCRF). Information about AE and SAE will be collected at health centers on paper CRFs.

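### Non-serious systemic reactions at the vaccination site fall outside the stated AE outcome, and the plan gives no on-site reaction a written route to the AE/SAE form

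*Combined protocol and SAP*

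**What the plan says.** **Scope.** SAP 3.2.2.3 deals with immediate reactions in one sentence: "Immediate reactions post-vaccination will be collected as other AE(s) from previous section". The previous section, SAP 3.2.2.2, says "In this study, the recording AEs will be limited to injection-site reactions as site pain injection, redness, swelling, itchiness, infection, etc". Protocol section 8 agrees: "In this trial, the recording of AEs will be limited to the evaluation of injection-site reactions (pain, tenderness, induration, infection, etc"). SAP 3.2.2 names the safety outcomes as injection-site AEs to 7 days and SAEs to 28 days. Protocol 6.1, under vaccine safety, is wider and promises that all AEs and SAEs are recorded.

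**Place.** Protocol 7.10 says "Immediate reactions post-vaccination will be treated free of charge on-site by trained clinical staff", but mentions no record. Protocol 11.1 says "Information about AE and SAE will be collected at health centers on paper CRFs". Protocol 9.10 says "No individual information will be collected at vaccination sites". The site record that the protocol describes is a count: "The number of doses of vaccine administered at each site will be noted on tally sheets" (protocol 7.6.3).

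**Content and output.** For each AE, SAP 3.2.2.2 asks for intensity, dates, outcome, causality, age and sex. SAP 4.3.3 tabulates non-serious AEs to 7 days, SAEs, and SAEs leading to death. Neither it nor the tables and listings in SAP sections 5 and 6 has an entry for immediate reactions.

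**The concern.** Take a child who faints or develops generalised urticaria minutes after the injection, is treated on the spot, is not judged to have had a serious event, and goes home. The reaction is not at the injection site, so it is not a recordable AE under SAP 3.2.2.2. It is not an SAE either. The child has recovered and has no reason to attend the health centre where the forms are kept. A local reaction in the same setting is within scope, but it too has no described path from the vaccination site to a form.

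Reactions within minutes of an injection are among the easiest to attribute to it. The product is licensed up to 2 years of age (protocol 7.2) and is given here to children aged 1-9 at two dose levels. Protocol 7.2.1 lists several systemic reactions among the most frequent. The secondary safety objective speaks of AEs over 7 days with no injection-site limit, so a 7-day table that omits this class of event answers less than the objective asks.

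**Working it through.** There is no planned figure to reproduce, and the point does not depend on one. The check is to follow each kind of on-site reaction through the rules.

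| Reaction at the vaccination site | In a recorded category? | Written route to a form? | In a planned table? |
|---|---|---|---|
| Local, not serious | Yes, AE (SAP 3.2.2.2) | None described from the site | Yes, if it reaches a form |
| Systemic, not serious | No, under SAP 3.2.2, SAP 3.2.2.2 and protocol 8; yes, if protocol 6.1 or a wide reading of SAP 3.2.2.3 prevails | None described from the site | No, under the stated outcome |
| Serious, local or systemic | Yes, SAE (protocol 8, SAP 3.2.2.1) | To the sponsor within 24 hours of awareness (protocol 8.4.1); the step from site to form is not written | Yes (SAP 4.3.3, 5.3) |

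Four pairs of statements do not fit together:

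1. Protocol 6.1 (all AEs) against protocol 8, SAP 3.2.2 and SAP 3.2.2.2 (injection-site AEs only).
2. SAP 3.2.2.3 (immediate reactions are collected) against the limit in the section it refers to.
3. SAP 3.2.2.2 (age and sex for each AE) against protocol 9.10 (no individual information at the sites), for any AE that begins and ends on site.
4. Protocol 7.10 (treatment on site) against protocol 11.1 (forms at health centres), with no transfer step between them.

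On size, the planned target is 54 clusters × 600 children = 32,400, that is 27 × 600 = 16,200 in each dose arm (protocol 7.1). These are children targeted, not doses given. The documents state no rate of immediate reactions, so no count of missed events follows.

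**The case against.** The strongest reply is that SAP 3.2.2.3 does not import the injection-site limit at all. SAP 3.2.2.4 uses nearly the same phrase for deaths, which are plainly not confined to the injection site. There the phrase means the AE form and its data fields. Read the same way, SAP 3.2.2.3 puts every immediate reaction on the AE form, which also fits protocol 6.1. This reading is reasonable. It is not stated, however, and SAP 3.2.2 would still define the AE outcome as injection-site only.

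Protocol 9.10 may also mean only that no routine register is kept. Consent can be signed at the site (protocol 9.9.2), and vaccinees are to be summarised by sex and age group (SAP 4.3.1), so a literal bar is hard to sustain. A study health professional sits at the nearest health centre for 28 days, and community health workers are asked to pass on any events. AE definitions and the management of hypersensitivity reactions are left to SOPs, which may supply a form. All this makes some capture likely. It does not supply a written on-site step, and an SOP should not have to override a limit set in both protocol and SAP.

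Three stronger inferences are not supported:

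- A reader might infer that all on-site systemic reactions go uncounted. Serious ones are counted: the SAE definition has no injection-site limit and includes important medical events.
- A reader might infer that the count of non-serious systemic reactions must be zero in both dose arms. That holds only if the narrow reading of SAP 3.2.2.3 is the intended one.
- A reader might multiply 32,400 by a plausible rate and report a number lost. Both the rate and full uptake would be assumptions without a basis in the documents.

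The SAP abbreviation list includes an immediate adverse event, but the term is not used in the SAP sections on safety assessment, analysis, tables or listings, and sections 5 to 7 still carry template prompts. It is weak evidence of intent.

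**Conclusion.** The point holds in a limited form. As written, non-serious systemic reactions at the vaccination site lie outside the stated AE outcome, and no section describes how any on-site reaction reaches the AE/SAE form. The documents contradict themselves on both matters, so the text needs reconciling whichever meaning was intended.

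The effect is confined to the 7-day AE results in the two dose arms. The carriage endpoint is untouched, and serious reactions are within scope as SAEs. The size in events cannot be estimated. The conclusion rests on the protocol and SAP alone; the SOPs were not available and could close part of the gap in practice. This is a cheap improvement to a stated safety objective, not a defect in the trial's main comparison.

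**What to change.** Reconcile protocol 6.1, 8, 9.10 and 11.1 with SAP 3.2.2, 3.2.2.2 and 3.2.2.3:

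- **Scope (protocol 6.1 and 8; SAP 3.2.2 to 3.2.2.3).** State that any reaction seen or treated at the vaccination site, local or systemic, is recorded on the existing paper AE/SAE form. The injection-site limit can remain for other non-serious AEs up to day 7 if that is the intention, with protocol 6.1 worded to match.
- **Place (protocol 11.1).** Add vaccination sites to the places where the form may be completed.
- **Privacy (protocol 9.10).** Make children with a reaction an exception to the rule on individual information.
- **Output (SAP 5.3).** Report immediate reactions by dose arm as a separate row of Table 3.1, the AE summary. The SAP gives the same number to the SAE summary, so the row should be tied to the table's title.

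The cost is wording in these sections, copies of an existing form at the vaccination sites, a few more forms, and identifiable data for those children only. Trained clinical staff are already to be on site under protocol 7.10. The change concerns recording and reporting alone.

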3.2.2.4 Fatal adverse events

Any event which results in death will be recorded in the AE CRF as other AE from previous section.

Additional information will be reported in the Serious Adverse Event form as the expectedness of the event, the result of the verbal autopsy and all relevant clinical records to provide a complete narrative of the fatal event.

3.2.3 Other Assessments

During both surveys, other information on the households will be collected, including a household census including members' age and sex, the type of residence, occupation of the head of household, highest level of education of the head of household, ethnicity of the head of household, and information about known risk factors for pneumococcal carriage, including exposure to solid fuel smoke, certain indoor cooking practices, and smoking habits.

During the baseline survey only, one randomly-selected household member will be administered a detailed questionnaire about social contacts with people of different ages, their sleeping arrangements, and their level of educational attainment.

During both surveys, one randomly-selected child aged 1 to 9 years will have a NP swab collected. Information will also be collected regarding this child's age, sex, sleeping arrangements, PCV vaccination status, and recent medical history, including medications taken in the last 14 days.

During the follow-up survey only, all children in the target age group for the vaccination campaign will be asked about their participation in the vaccination campaign.

During the vaccination campaigns, the number of children vaccinated will be collected at each site.

4. Statistical Methods

4.1 Timing of Analysis

Determining whether mass campaigns with fractional dose PCV10 would accelerate herd protection against pneumococcal transmission in Sub-Saharan Africa

The primary endpoint will be the change from baseline in VT carriage at 6 months post-vaccination campaign. The reduction in VT carriage will be calculated by comparing the proportion of children carrying VT pneumococci 6 months post-vaccination to the baseline.

4.1.1 Primary Analysis Time Point

The primary analysis time point for the primary endpoints is 6 months post vaccination campaign.

4.2 Methods for Handling Missing Data

In general, missing data will be considered missing at random and no imputation will be performed.

4.3 Statistical Analysis

All results will be displayed by intervention group (full dose, fractional dose or control).

Descriptions of the study population will be provided at the individual level and at the cluster level as appropriate. Statistical analyses to demonstrate superiority and non-inferiority will be performed at the individual level. Non inferiority will be tested if the superiority of the full dose is shown; therefore, no adjustment for multiplicity is necessary.

Comparison between groups will be done at the cluster level using Student's t-test for continuous variables and Chi square test (or Fisher's exact test if more appropriate) for categorical variable.

Safety analysis will be done at the individual level only, and comparison for categorical variables will be done using a Chi square test (or Fisher's exact test if more appropriate). All comparisons will be done at the 0.05 significance level.

Prevalence of carriage will be presented with a 2 sided 95% confidence interval.

All statistical analysis will be performed on the statistical software Stata version 17 or later.

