Safety analysis will be based on the entire study population. Safety and tolerability of PCV10 will be assessed by comparing the frequency (%) of AEs and SAEs in full-dose and fractional-dose arms to the control arm using the Fisher's exact test. Safety data will be presented in tabular and/or graphical

format and summarized descriptively. Data will be analyzed according to an intention-to-treat approach. In the unlikely event of clusters receiving incorrect interventions, or being only partially vaccinated, per-protocol analyses will be repeated on the primary endpoint.

13 Quality assurance and control

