3.1.1 Study cohorts

Clusters will be randomized to full dose mass vaccination campaigns, fractional dose mass vaccination campaigns or the control arm in 3:3:1 allocation ratio. Clusters will be composed of a village or group of closely-neighbouring villages that share a school or market, and will be limited to a population of between 500 and 4000 persons. Stratified randomization will be used to account for proximity to the nearest health centre (<5 km vs ≥5 km). In the event of significant imbalance in carriage of VT pneumococci between clusters in the baseline survey, randomization may also be stratified by baseline prevalence upon the decision of the Trial Steering Committee. For this reason, randomization will happen after the results of the baseline survey are known.

Vaccination will target all children aged 1 to 9 years of age residing in the selected villages. (If baseline survey data unexpectedly shows very low prevalence of carriage at the extremes of this age range, the target age group may be adjusted upon recommendation of the trial steering committee.) We estimate that children eligible for the vaccination campaigns will represent 30% of the total population. With an estimated average of 2000 people per cluster, vaccination will target approximately 600 children 1-9 years of age in each cluster receiving vaccine. In total, in the 54 clusters receiving vaccine, the mass vaccination campaign with single full- or fractional-dose PCV is expected to target approximately 32,400 children 1-9 years of age.

Prior to the mass vaccination campaign, a cross-sectional survey will be implemented to estimate community-level carriage of VT pneumococci, as well as to collect data on household composition, social interactions and PCV vaccination coverage in the routine EPI. A total of 36 households in each cluster will be invited to participate in the cross-sectional survey. For the purposes of this study, a household is defined as a group of people living under the authority of a head of household, sleeping under the same roof, and sharing at least one meal per day, for at least two weeks, independent of any family ties. Selection of households will be based on probability sampling. The required number of households in each cluster will be randomly selected using simple random sampling based on an exhaustive list of heads of household in the cluster.

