3.1.3 Randomization and Blinding

Following the results of the baseline survey, clusters will be randomized in a 3:3:1 ratio, with 27 clusters randomized to receive a campaign with the full dose, 27 clusters randomized to receive a campaign with the fractional dose and 9 clusters randomized to the control arm. Randomization will be stratified by proximity to nearest health center (<5 km vs ≥5 km). In the event of significant imbalance in carriage of VT pneumococci between clusters in the baseline survey, randomization will also be stratified by baseline prevalence, after a decision by the trial steering committee. An equal or proportional number of clusters will be randomized to each study arm from each stratum. The study statistician randomization will prepare the material to generate the list (blocked randomization with fixed block size if only one stratum, by minimisation if more than one stratum), and the final list will be generated by an independent statistician who has no contact with study participants. Study implementation will be blinded to the extent possible. Vaccination nurses will not be blinded to the vaccine they are giving, but they will not communicate vaccine allocation to other members of the team or to participating villages. Villages randomized to the control arm will not receive any “dummy” intervention, so will not be blinded to their group allocation. The trial will be observer-blind in that personnel at KWTRP will be blinded to group allocation until after the completion of culture and serotyping in each survey.

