4.3.3 Safety Analysis

Safety analysis will be based on the entire study population.

Any adverse events occurring within 7 days after vaccination, serious adverse events, or deaths will be summarized as n (%) of participants having experienced the AE(s), and SAEs or death by arms. Comparisons will be done between full-dose and fractional-dose arms with the control arm, using a Fisher's exact test.

All AEs will be coded to a "Preferred Term" (PT) and primary associated "System-Organ Class" (SOC) according to the MedDRA dictionary (Medical Dictionary for Regulatory Activities, version 25.0).

Counts and proportions will be provided overall and for each PT within each SOC. AE(s) will be tabulated overall and by grade, and by type of AEs:

- AEs non SAEs occurring with 7 days after vaccination
- SAEs
- SAEs leading to death

5. Statistical Tables to be Generated

<Consider appropriate tables for each of these categories and some examples are provided>

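### Safety differences are tested child by child although clusters of about 600 children were randomised, so p-values for SAEs and deaths may be too small, by an amount the documents do not determine

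*Combined protocol and SAP*

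**What the plan says.** SAP 4.3 sets the rule for safety: "Safety analysis will be done at the individual level only, and comparison for categorical variables will be done using a Chi square test", with Fisher's exact test as the alternative. The level is given in the same section: "All comparisons will be done at the 0.05 significance level". SAP 4.3.3 names the contrast: "Comparisons will be done between full-dose and fractional-dose arms with the control arm, using a Fisher's exact test". Protocol section 12 has the same plan, "comparing the frequency (%) of AEs and SAEs in full-dose and fractional-dose arms to the control arm using the Fisher's exact test". None of these sentences mentions clustering.

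The unit of allocation is the cluster. SAP 3.1.3 has 27 full-dose clusters, "27 clusters randomized to receive a campaign with the fractional dose and 9 clusters randomized to the control arm". SAP 3.1.1 gives their size: "vaccination will target approximately 600 children 1-9 years of age in each cluster receiving vaccine".

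Elsewhere the SAP does allow for clustering: GEE for the carriage outcome and robust standard errors for the risk-factor models (4.3.2.1), and adjusted tests for baseline proportions (4.3.1).

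**The concern.** Chi-square and Fisher's exact tests assume that children's outcomes are independent. Here about 16,200 vaccinated-arm children (27 × 600) would be set against about 5,400 controls (9 × 600, if control clusters are of similar size), while only 36 units were allocated.

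Independence is hard to defend. Events reach the study through passive surveillance by staff at the nearest health centre and by village community health workers (protocol section 8, SAP 3.1.4), and protocol 9.5 accepts that this may under-report. The control-arm SAE window runs from the first vaccination to 28 days after the last in the same health-facility catchment, so its length can differ between catchments. Background illness may also differ between villages.

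If event risk varies between clusters, the tests understate the variance of the difference between arms. A chance difference in either direction could then be reported as a safety signal for full or fractional dosing, in a trial meant to inform policy on dose sparing.

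**Working it through.** **The plan's own figure.** The documents give no sample size, power, event rate or ICC for safety. The figure they do give, for carriage, is reproduced with clustering included. For 27 × 36 children per arm at ICC 0.02, the design effect is DE = 1 + 35 × 0.02 = 1.70, and the effective n is 972 / 1.70 = 572 per arm. SE = √(2 × 0.15 × 0.85 / 572) = 0.0211, and power = Φ(0.075 / 0.0211 − 1.96) = 94%, consistent with the stated minimum of 90%. The plan thus allows for clustering in its design but not in its safety tests.

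**Inputs for safety.**
- From the documents: 27 versus 9 clusters, about 600 children per cluster, level 0.05 (taken as two-sided).
- Assumed: event risk p from 0.02% to 0.5%, and between-cluster coefficient of variation (CV) of risk from 0.5 to 1.0.

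**Formulas.**
- ICC = CV² × p / (1 − p)
- DE = 1 + 599 × ICC
- Approximate true size = 2 × (1 − Φ(1.96 / √DE))

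Example: p = 0.5% and CV = 1.0 give ICC = 0.005 / 0.995 = 0.00503, DE = 1 + 599 × 0.00503 = 4.01, and size = 2 × (1 − Φ(0.979)) = 33%.

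The formula ignores the discreteness of Fisher's test, which makes it conservative when events are few. The last column therefore comes from simulation under no true difference (27 versus 9 clusters, gamma-distributed cluster risks). Ranges run from CV 0.5 to CV 1.0.

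| Event risk | Expected events, vaccine arm / control | DE | Size by formula | Simulated size of Fisher's test |
|---|---|---|---|---|
| 0.02% | 3.2 / 1.1 | 1.03-1.12 | 5.3-6.4% | about 2% |
| 0.05% | 8.1 / 2.7 | 1.07-1.30 | 5.9-8.6% | about 3-6% |
| 0.1% | 16.2 / 5.4 | 1.15-1.60 | 6.8-12.1% | about 6-9% |
| 0.2% | 32.4 / 10.8 | 1.30-2.20 | 8.6-18.6% | about 8-17% |
| 0.5% | 81 / 27 | 1.75-4.01 | 13.9-32.8% | about 13-33% |

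With no between-cluster variation, Fisher's test holds its level: 4-5% at the commoner risks and about 1% at 0.02%.

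**Upper illustration.** At ICC 0.02, DE = 1 + 599 × 0.02 = 12.98 and the formula gives a size of 59%. That ICC describes meningococcal carriage (protocol 7.12). At p = 0.1% it would need CV = √(0.02 × 0.999 / 0.001) = 4.5, far above the range assumed here.

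**Candidate replacements, under the same null.** A Welch t-test on cluster risks rejects in about 9-11% at 0.02% risk and about 9% at 0.05%; it comes to 5-7% only at about 0.2% and above. A permutation test on cluster risks stays at or below about 5% throughout.

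**AEs against control.** SAP 3.2.2.2 limits AEs to injection-site reactions. Control villages receive no injection and no dummy (SAP 3.1.3), and only SAE collection is described for them (SAP 3.1.4 and 3.2.2). That comparison has no usable comparator, whatever the clustering.

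**The case against.** The strongest reply has four parts.

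1. **The inflation may be absent where it matters most.** The protocol calls serious reactions rare and gives no rate. At 0.02-0.05% risk Fisher's test is at or below its nominal level, or barely above it. This stands. A reader might infer from the carriage ICC that more than half of null safety tests would be significant, or that the p-values are far too small in general. The documents support neither, because they contain no safety ICC.

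2. **The effective sample is not nine.** A reader might infer that the control arm carries only nine observations. That is so only at ICC = 1. With 5,400 control children the effective number is about 3,377 at ICC 0.001 and 416 at ICC 0.02. Moreover, a health centre usually serves 10-20 villages (protocol 7.3), so some reporting differences may be shared across arms. This also stands.

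3. **The protocol may already cover it.** Section 12 says in general terms that outcome analyses control for clustering and that comparisons of proportions are adjusted for it, and protocol 6.1 lists vaccine safety among the outcomes. At protocol level this leaves ambiguity. It does not rescue the SAP, which restricts safety to the individual level and names unadjusted tests.

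4. **Little depends on these p-values.** The safety objective is to assess occurrence, and protocol section 12 says that safety will be summarised descriptively. There is no safety hypothesis, margin or stopping rule tied to the tests. This stands and limits the severity. A reader might also infer that the carriage results are affected; they are not, since GEE is specified for them.

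**Conclusion.** The concern holds in a limited form. The safety tests specified in SAP 4.3 and 4.3.3 do not match the cluster allocation, and where risk varies between clusters they understate the uncertainty. The p-values for SAEs and deaths, and for any full versus fractional AE comparison, may be too small. Under an assumed CV of 0.5-1.0 with 27 versus 9 clusters of about 600, the true size of the nominal 5% Fisher test runs from no excess at the rarest risks to about a third at 0.5%. Both the CV and the event risks are assumptions. The vaccine-arm denominator is vaccinated children, so somewhat fewer than 600 per cluster, which lowers the figures slightly.

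The AE-versus-control test fails for a different reason, the missing comparator. Overall this should be fixed before analysis, but it does not threaten the trial's main conclusions.

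**What to change.** In SAP 4.3 and 4.3.3, and in protocol section 12 for consistency:

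- Replace the individual-level rule with a comparison of cluster-level SAE and death risks by permutation test, permuting within the distance strata (and any baseline-prevalence strata actually used). Do not substitute a Welch t-test, which is too liberal for rare events.
- Report the risk difference with a cluster-based 95% CI, for example by inverting the permutation test.
- State in advance a minimum event count below which only counts and rates are reported, without a p-value. The expected counts in the table above can guide the choice; it must not be made after seeing the data.
- Drop the AE-versus-control test. Compare injection-site AEs between the full and fractional arms by the same cluster-level method.

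No new data are needed: site tally sheets give the numbers vaccinated and the census gives the control denominators. The cost is wording and modest programming. The price is wider intervals and fewer nominally significant safety results.
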